7.2 SCREENING PHASE

Assessments performed exclusively to determine eligibility for this study will be done only after obtaining informed consent. ***Assessments performed for clinical indications (not exclusively to determine study eligibility) may be used for baseline values even if the studies were done before informed consent was obtained.***

All screening procedures must be performed within 28 days prior to registration, unless otherwise stated. The screening procedures include the following: (See Table 7.1 above for the list of assessments to be performed.)

7.2.1 Informed Consent

Patients must provide a signed informed consent form prior to any study specific evaluations including screening. Eligibility will be determined according to the inclusion/exclusion criteria as described in Section 5. A list of procedures to be performed at time of screening is summarized in Table 7.1. Patients must meet all eligibility criteria to be considered for enrollment in the study.

7.2.2 Eligibility Checklist (Inclusion/Exclusion)

In order to determine and confirm the eligibility of the patient, once all screening procedures are completed, an eligibility checklist must be completed by the research team prior to chemoembolization.

7.2.3 Patient Demographics and other Baseline Characteristics

The data that will be collected on patient characteristics at screening includes:

- Demographic (name, date of birth, age), sex, race/ethnicity;
- Diagnosis, RB status, and extent of cancer (staging) – tissue biopsy (required);
- Pertinent Medical History;
- Prior cancer treatment;
- All medications taken within 30 days before first treatment. If there are any changes, medications are to be updated on a continual basis.

Furthermore the following assessments will be performed:

- Vital Signs (BP, HR, T, RR);
- Adverse Events / Conmeds
- Height and Weight;
- Physical Examination (PE);
- ECOG Performance Status (PS);
- Laboratory Evaluations (chemistry, CBC, PT/INR, Lipid Panel, and UA)
- ECG (in Triplicate – baseline only)
- ECHO or MUGA;

- Radiological Assessments (RECIST 1.1) (CT - chest/abdomen/pelvis or MRI – abdomen/pelvis). Chest CT will be performed at baseline only. During the treatment phase, a Chest CT will be performed as clinically indicated;
- Pregnancy Test (Women of Child-bearing Potential Only).

7.2.4 **Pre-Treatment - Biomarker Tissue Biopsy (Required)**

After signing the treatment and biopsy informed consent, the screening biopsy, confirming HCC diagnosis, staging, and (RB+) result, must be complete within 28 days prior to registration unless the patient has archival formalin fixed paraffin embedded tissue to determine RB status. This biopsy is required to confirm patient eligibility. However, initial TACE procedure can be initiated prior to determination of RB status provided informed consent is signed and biopsy tissue is available for analysis.

7.2.5 **Biomarker / DNA Blood Collection (Optional – Phase II only)**

After signing the optional biomarker / DNA consent for future biomarker and DNA blood, samples will be collected at baseline, during treatment, and at the end of treatment or early-term visit. This procedure is for research and will not be used to make medical decisions regarding the patient's treatment.

7.3 **TREATMENT PHASE**

7.3.1 **Study Treatment**

Patients will be treated with chemoembolization once every 4 weeks (or every 28 Days), for a total of up to 4 chemoembolizations within the first 6 months.

In addition, patients will be treated with 200, 400, or 600 mg LEE011 once daily by mouth (3 Weeks on / 1 Week off in a 28 day cycle) until disease progression, unacceptable toxicity, death, or discontinuation from the study treatment due to any other reason. For details of assessment, refer to Table 7.1.

7.3.2 **Post-Treatment – Biomarker Tissue Biopsy (Optional – Phase II only)**

The post treatment biopsy is optional and the patient must have consented to this second procedure during the initial consenting process. The second biopsy, for research purposes only, will be performed between Weeks 8 and 9 post initial treatment of LEE011. To qualify for the second biopsy, patients must have taken LEE011 for 21 consecutive days (21 days on treatment / 7 days off in a 28 day cycle) and had at least one chemoembolization.

7.3.3 **Additional Treatment Phase Assessments will be performed:**

- Vital Signs (BP, HR, T, RR);
- Adverse Events / Conmeds
- Weight;

- Physical Examination (PE);
- ECOG Performance Status (PS);
- Laboratory Evaluations (chemistry, CBC, PT/INR, and Lipid Panel);
- ECG;
- Radiological Assessments (RECIST 1.1) (CT - chest/abdomen/pelvis or MRI – abdomen/pelvis). During the treatment phase, a Chest CT will be performed as clinically indicated;

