7.0 VISIT SCHEDULE AND ASSESSMENTS

Table 7.1, lists all of the assessments and indicates with an “X”, the visits and when they are performed. For the phase Ib component only the first cycle will be utilized for determination of dose limiting toxicities. All data obtained from these assessments must be supported by the proper source documentation and placed in the patient’s chart.

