7.1 TABLE OF ASSESSMENTS

Treatment Days	Screening Phase ¹		Treatment Phase: Chemoembolization	Treatment Phase: LEE011						Post Treatment Follow-up			Survival Phase
	Day -28 – Day -1	Day -7 – Day -1	7-14 days Following chemoembolization	Cycle 1		Cycle 2		C3	C4+	End of Treatment or Early Withdrawal (Within 15 Days of Last LEE011 Dose)	Safety Follow-Up (Within 30 Days of Last LEE011 Dose)	Efficacy Follow-Up	Survival Follow-Up Every 12 weeks
Visit Assessments				Day 1 ^{2,13}	Day 15	Day 1	Day 15	Day 1	Day 1				
Informed Consent	X												
Demographics	X												
Eligibility Checklist - Inclusion / Exclusion	X												
Med History	X												
Dx and Extent of Cancer (Staging)	X												
Physical Exam		X	X	X	X	X	X	X	X	X	X		
ECOG Status		X	X	X	X	X	X	X	X	X	X		
Height	X												
Weight		X		X	X	X	X	X	X	X	X		
Vital Signs		X	X	X	X	X	X	X	X	X	X		
CBC		X	X	X	X	X	X	X	X	X	X		

Chemistry (CMP)		X	X	X	X	X	X	X	X	X	X			
Cholesterol/Lipid Panel		X		X	X	X	X	X	X	X	X			
PT/INR		X	X	X	X	X	X	X	X	X	X			
Serum Pregnancy Test (WOCBP Only)		X							X	X				
Urinalysis		X								X	X			
Tumor Assessments with RECIST 1.1 ⁵	X			←----- Every 8 weeks ⁵ ----- -----→									X ⁵	
ECHO/MUGA	X													
ECG (12 – Lead)		X ³		X	X	X	X ³	X	X	X	X			
Adverse Events ⁶	X	X		X	X	X		X	X	X	X			
Conmeds ⁶	X	X		X	X	X		X	X	X	X			
Biomarker Tissue Collection (Biopsy) ⁷	X ⁷					X ⁷								
Biomarker Blood Collection ⁸		X		X		X		X	X	X				
LEE011 Study Drug (Oral) ⁹				X		X		X	X					
Patient Dosing Diary for LEE011 ⁹				X		X		X	X					
Chemoembolization (TACE) ¹⁰				X		X		X	X					
Discontinuation ¹¹											X			
Survival Follow-Up ¹²													X	

1. Screening assessments, apart from those listed above, must occur within 28 days of registration as per Table 7.1;
2. Vital Signs, ECOG Performance Status, Physical Exam, ECG, CBC, CMP, PT/INR, Lipid Panel, Serum Pregnancy Test (WOCBP Only), and Urinalysis should be performed within 7 days of the first treatment day (Cycle 1, Day 1). If there are any dose modifications or halting of drug in the phase II aspect, weekly hematology, comprehensive metabolic panels, and PT/INR laboratory investigations will be performed until the grade of adverse event leading to the modification or cessation is stable or a grade reduction occurs. In addition, following each chemoembolization the following will be done every other week for two cycles after each chemoembolization: physical examination, CMP, CBC, and PT/INR.

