3. In order for an accurate evaluation of baseline QTc, a total of three (triplicate) 12-lead ECGs will be performed after resting in a supine position for 5-10 min, with a 2 minute interval between each ECG (triplicate ECG's at screening only). Subsequent ECG's will be performed after resting in a supine position for 5-10 min, on Day 1, C1D15, and C2D15 of each treatment cycle (single ECG's)prior to chemoembolization and LEE011;

4. For all treatment visits there is a general +/- 3 day window on assessments to take into account scheduling over public holidays, if not specifically specified otherwise;
5. Baseline scans can be completed within 28 days prior to registration. After baseline, radiological assessments (CT –chest/abdomen/pelvis or MRI – abdomen/pelvis) must be performed as outline in Table 7.1 (Every 8 weeks during the treatment phase). CT Chest must be performed at baseline. CT Chest during treatment will be performed if clinically indicated. A visit window of +/- 7 days is allowed. Once the patient has been discontinued from the study and enters the efficacy phase, radiological assessments (CT or MRI) will continue on the every 8 weeks schedule until progression or for the first 12 months, whichever comes first. After a year, radiological (CT or MRI) assessments will be performed every 12 weeks until progression.
6. AE/Conmeds will be assessed from consent until up to 30 days last dose of LEE001 or until resolution, whichever comes first. Conmeds will recorded up to 30 day prior to consent;
7. The biopsy performed during screening is for HCC diagnosis and RB positive status and must be performed for the subject to be eligible for the study. However, initial TACE can be performed following agreement of informed consent while RB proficiency is being determined. If patient is not RB proficient patient will be removed from the study as a screen failed and offered other treatment. If the patient has archival formalin fixed paraffin embedded tissue no additional baseline biopsy will be done. The post treatment biopsy is optional and for research purposes only (phase 2 only). If the subject consented to the research biopsy during the consent process, it will be performed during the 8th and 9th week of after initiating treatment of LEE011 and at least one chemoembolization. NOTE: LEE011 should be held for 24-48 hours prior to and after the second biopsy. These held doses will not be made up and noted on the patient's diary.

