8. Biomarker blood collection is also an optional research procedure and the patient must have consented to the additional blood collection to participate (phase II only). Blood will be collected according to the schedule in table 7.1;
9. Patients will be treated with LEE011 (3 weeks on / 1 week off of a 28 day cycle) until disease progression, unacceptable toxicity, death, or discontinuation from the study treatment due to any other reason. The patient will complete a subject dosing log in order to ensure drug compliance. The patient will be provided a new dosing diary at each new treatment cycle and reviewed at the end of each cycle for compliance.
10. Patients will be treated with chemoembolization with up to 4 total chemoembolizations within the first 6 months from the initial chemoembolization.
11. Patients who discontinue treatment for reasons other than disease progression, death, start of new anti-neoplastic therapies, lost to follow-up, or withdrawal of consent to efficacy follow-up, then tumor assessments and patient reported outcomes must continue to be performed every 8 weeks during the first 12 months and every 12 weeks thereafter until the start of new anti-cancer therapy, disease progression, death, lost to follow-up, or withdrawn consent to efficacy follow-up;
12. All patients will be followed for survival status every 12 weeks regardless of treatment discontinuation until death, lost to follow-up, or withdrawal of consent to survival follow-up. Survival follow-up assessment may be made by a phone call to the patient or designated PHI, EPIC medical record review, or certified mail. At least 3 documented attempts should be made to contact the patient before the patient is considered lost to follow-up.
13. The follow-up visit after chemoembolization can be used as day 1 visit of each cycle if the decision is made to continue with LEE011 treatments.

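### Table 7.1 marks TACE on LEE011 Day 1 in every cycle, against the 7-day minimum in 6.12, and no unconditional hold or express minimum gap is stated for a repeat TACE

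*Combined protocol and SAP*

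**What the plan says.** Section 7.0 explains that the X marks in Table 7.1 indicate "the visits and when they are performed". The TACE row is marked at Day 1 of cycles 1, 2, 3 and 4+, exactly where the LEE011 row is marked. No TACE mark stands before cycle 1 Day 1 (C1D1). The column just before C1D1 is headed "7-14 days Following chemoembolization". Footnote 3 places the on-treatment ECGs "prior to chemoembolization and LEE011".

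Section 6.12, in the part on giving LEE011 with chemoembolization, lets LEE011 start no sooner than 7 days after TACE, once laboratory, toxicity and performance-status criteria are met. Patients who cannot start within 28 days of the initial TACE are removed. The same part requires AST, ALT or alkaline phosphatase raised after TACE to return to baseline grade before LEE011 is started or continued.

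For repeat TACE:
- Section 6.12.7 allows it where indicated, at least 4 weeks apart, up to 4 in six months, subject to toxicity, creatinine and bilirubin limits.
- Section 7.3.1 says: "Patients will be treated with chemoembolization once every 4 weeks (or every 28 Days), for a total of up to 4 chemoembolizations" in the first six months.
- Footnote 13 says: "The follow-up visit after chemoembolization can be used as day 1 visit of each cycle", if LEE011 is to continue.
- Footnote 2 covers monitoring: "the following will be done every other week for two cycles after each chemoembolization".
- For a different procedure, the optional research biopsy, footnote 7 does state a hold: "LEE011 should be held for 24-48 hours prior to and after the second biopsy".

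Section 6.12.3 lists midazolam (as Versed) and fentanyl for sedation. Section 6.9 and Appendix Table 2 prohibit fentanyl during study treatment, as a CYP3A4/5 substrate with a narrow therapeutic index.

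**The concern.** Section 7.3.1 sends staff to Table 7.1 for the details of treatment visits. A site working from that table would give TACE and LEE011 on the same day, which 6.12 rules out for the start of LEE011 and which no text expressly rules out later.

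Section 9.2 expects raised liver enzymes after TACE. Under Table 6-5, a rise in AST or ALT from baseline grade 0 or 1 to grade 3 ends LEE011. In cycle 1 of phase Ib the same rise is a dose-limiting toxicity (DLT) if it is even possibly related to LEE011 (Table 6.2). Where LEE011 is taken on the day of a repeat TACE and the days after it, the two sources of liver injury overlap. The sedation instruction and the prohibited-medication list also cannot both be followed at a repeat TACE in a patient on LEE011.

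**Working it through.** The plan states no figure to reproduce here, so the check is a comparison of texts and calendar arithmetic.

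**1. First TACE.** As marked, TACE and LEE011 fall together on C1D1, a gap of 0 days. Section 6.12 requires at least 7. The table's own post-TACE column, placed before C1D1, requires TACE to have come earlier. The table therefore contradicts both 6.12 and itself. (The table was read from extracted text, but the TACE and LEE011 rows have the same cell positions and line up with the other rows.)

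**2. Repeat TACE on day 28.** Inputs: first TACE on day 0; LEE011 starts on day L, with 7 ≤ L ≤ 28 (6.12); dosing on cycle days 1-21 and rest on days 22-28 (6.3); repeat TACE no sooner than day 28 (6.12.7), which is also the interval in 7.3.1. Assume no LEE011 interruption.

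Cycle 1 day of a day 28 TACE = 28 − L + 1 = 29 − L.
Cycle 1 doses scheduled on or after that day = 21 − (29 − L) + 1 = L − 7.

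| L | Cycle 1 day of TACE 2 | Doses on or after it |
|---|---|---|
| 7 | 22 (first rest day) | 0 |
| 10 | 19 | 3 |
| 14 | 15 | 7 |
| 28 | 1 | 21 |

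Only L = 7 avoids a dosing day. All four cases lie inside cycle 1, the DLT window.

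**3. Later repeats.** TACE 2 still lands on a cycle 1 dosing day up to day L + 20: days 28-30 for L = 10, days 28-34 for L = 14. It leaves cycle 1 from day L + 28: day 35, 38 or 42 for L = 7, 10 or 14.

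**4. Table 7.1 followed at C2D1.** TACE 2 is on day L + 28, which is day 35 to 42 for L = 7 to 14. That satisfies the 4-week minimum in 6.12.7 but not the 28-day interval in 7.3.1, and its gap to LEE011 is 0 days.

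**5. Fentanyl.** Section 1.7.4.1 gives a mean effective half-life of 32.6 hours. Assuming simple exponential decline, the fraction of LEE011 left 24 hours after the last dose is 0.5^(24/32.6) = 0.60, and after 168 hours it is 0.5^(168/32.6) = 0.03. A hold starting on the TACE day would leave about 60% of the drug present, so it would not settle the conflict. LEE011 is also a time-dependent CYP3A4 inhibitor, so its effect may outlast these figures.

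**6. Cost of a gap of g days at a repeat TACE on cycle day d** (d = 29 means the next Day 1). Doses omitted = min(g, 22 − d), not below 0. Delay of the next Day 1 = d + g − 29, not below 0. For g = 7 the maxima are 7 doses (for example d = 15: min(7, 7) = 7) or 7 days (d = 29: 29 + 7 − 29 = 7). For g = 14 they are 14 doses (d = 8: min(14, 14) = 14) or 14 days (d = 29).

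**The case against.** The strongest reply is that the protocol already orders the two treatments. For the first TACE this is right. Section 6.12 describes a clinic visit 7-10 days after TACE, at which the decision to start LEE011 is made, and section 6.6 replaces patients who never start LEE011 after their initial TACE. A reader might infer from Table 7.1 that same-day treatment in cycle 1 was intended; the rest of the protocol does not support that. Footnote 3 can also be read as an ECG before whichever treatment is due.

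For repeat TACE, a reader might infer that nothing at all requires LEE011 to be held. That is also too strong. The enzyme condition in 6.12 is mandatory and applies to continuing as well as starting, so it reaches patients already on drug. Section 6.9 advises considering an interruption for caution-listed drugs needed briefly, and Appendix Table 1 lists both midazolam and doxorubicin. What remains is that the enzyme condition acts only once enzymes have risen, the 6.9 advice is discretionary and not tied to TACE, and footnote 13 only permits the safer order.

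A reader might further infer that DLTs cannot be attributed in phase Ib. The documents do not support this. Section 9.5 defines attribution categories, the lists of alternative causes are open-ended, and section 6.6 describes cohort 1 toxicity as TACE-related and not dose-limiting. A rule for events after a repeat TACE in cycle 1 would be added detail, and the overlap arises only if an early repeat is indicated.

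Finally, LEE011 is meant to suppress proliferation after embolization (1.5, 1.8), so dosing through a repeat TACE can be a legitimate choice. That stands against treating a compulsory hold as the only correct answer.

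**Conclusion.** Table 7.1 is wrong as written. Its earliest TACE mark gives a 0-day gap where 6.12 requires at least 7, and its C2D1 mark gives 0 days at a repeat TACE. The cycle 1 mark is a schedule error with a clear intended order. The repeat-TACE text has a real but narrower gap: conditional, permissive and advisory wording, with no unconditional hold or express minimum interval. A day 28 repeat falls on a dosing day for every LEE011 start after day 7, assuming no interruption and a repeat at the earliest permitted time. Section 7.3.1 omits the conditions in 6.12.7, although its cap of up to 4 shows that the 28-day interval is not compulsory. The fentanyl conflict is real at a repeat TACE; the first TACE precedes LEE011.

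The documents do not show that patients were treated on the same day, that phase Ib DLT counts are unreliable, or that a 7-day hold at every repeat TACE is required. The point should be corrected because Table 7.1 is the operational schedule and the correction is cheap.

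**What to change.** 1. In Table 7.1, move the first TACE mark ahead of C1D1.
2. Mark later TACEs as done if indicated, and place them before the post-TACE visit that serves as Day 1 under footnote 13, not in the LEE011 Day 1 cell.
3. Reword footnote 3 so that it no longer suggests TACE and LEE011 on one day.
4. Align 7.3.1 with 6.12.7: if indicated, at least 4 weeks apart, up to 4 in six months.
5. Resolve the fentanyl conflict, for example by an explicit exception for monitored procedural use or a different sedative. The choice is the sponsor's.

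These are text changes with no added patients or data.

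As an option, the sponsor could apply the 7-day gap and the 6.12 restart criteria to every repeat TACE. This changes the regimen. It costs up to 7 omitted doses or a delay of up to 7 days in the next Day 1 per repeat TACE, and up to 14 of either with a day 14 visit, which is within the 4-week interruption limit that 6.5 sets for toxicity. If adopted in phase Ib, the protocol should say whether a patient who omits cycle 1 doses for this reason (7 of 21 for L = 14 and a day 28 repeat) remains evaluable for DLT. If LEE011 is instead meant to continue through a repeat TACE, the protocol should say so.

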1.7.4.1 Clinical Pharmacokinetics of LEE011

LEE011 is rapidly absorbed with median T_{max} ranging from 2-5 hours in both adult and pediatric patients. Plasma concentrations increased approximately 2- to 3-fold from C1D1 to C1D18 due to accumulation, with steady state being reached by approximately day 8. Mean effective $T_{1/2}$ was 32.6 hours in study CLEE011X2101. At steady state (C1D18/21), plasma exposure increases in LEE011 were slightly higher than dose proportional over the dose range 50-1200mg.

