6.3 LEE011 ADMINISTRATION SCHEDULE AND DOSE ADJUSTMENTS

LEE011 will be given orally once a day on days 1-21 of a 28 day cycle (3 weeks on / 1 week off). Days 22-28 will be a “rest” from LEE011.

Table 6.1 Dose and Treatment Schedule

Study Treatment	Pharmaceutical form and route of administration	Total Dose	Frequency and/or Regimen
LEE011	200 mg capsules by mouth	200,400, or 600 mg	Once Daily on Days 1-21 of a 28 day cycle. Rest Days 22-28

LEE011 will be administered as a flat-fixed dose, and not by body weight or body surface area.

The investigators will instruct the patient to take the study drug as per protocol. Patients must be instructed to return unused study drugs to the site at discontinuation or completion of treatment. The site personnel will ensure that dosing compliance is being performed by reviewing patient dosing diaries at each the end/start of a new treatment cycle.

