11.0 CORRELATIVES STUDIES

Pathology Correlative Studies

A major obstacle to molecularly targeted chemotherapeutic agents has been obtaining relevant tumor tissue to measure the agents' biologic effects on target molecules or cellular pathways within the tumor. The utilization of sequential tumor biopsies to obtain tissue following treatment is well established in breast and colorectal carcinoma. (17) However, sequential tumor biopsies of liver tumors are less established due to a fear of procedural complications. The fear of bleeding events following liver biopsy of HCC appears unfounded and based on anecdotal evidence. A large, multi-institutional trial where patients with advanced chronic Hepatitis C underwent sequential liver biopsies demonstrated 16 cases (0.6%) of bleeding following 2740 liver biopsies. There were no deaths from peri-procedural bleeding and a platelet count under 60000 was identified as a risk factor. (18) Two large published series of core needle biopsy of HCC as a diagnostic measure report bleeding events in less than 1% of patients with no reported mortalities. In both series capsular location of HCC was associated with increased incidence of bleeding event. (19, 20) In this study all patients will potentially undergo up to two image-guided (either CT or Ultrasound) core needle biopsy of a single site of HCC at baseline (for clinical care) and between eight and nine weeks after the initiation of LEE011 (research only). The biopsy between eight and nine weeks following LEE011 initiation is not mandatory to initiate or continue with therapy and is subject to a separate informed consent. The baseline biopsy is needed to confirm HCC and RB positivity as an eligibility criterion. If archival formalin fixed paraffin embedded tissue is available for RB status analysis, a pre-treatment biopsy will not be required. To increase patient safety the following conditions must be met prior to liver biopsy:

- Platelet count $\geq 70,000$
- INR ≤ 1.8
- Target lesion not subcapsular in nature as determined by the participating interventional radiology team
- LEE011 will be discontinued for a period of 24-48 hours prior to biopsy

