There is no evidence that an image-guided liver biopsy following TACE increases risk of bleeding or tumor seeding. Due to the consideration that TACE is not considered a curative procedure and viable tumor tissue remains after an initial biopsy it is anticipated that enough tumor tissue will be available for the planned studies. (21)

The patient will sign the informed consent for participation in research liver biopsy prior to the procedure. The liver biopsy will be performed by radiologists and the ancillary staff of Department of Radiology following the standard clinical protocol, which includes obtaining a separate informed consent for the procedure itself. The core samples will be provided to the Department of Pathology for histological and RB status confirmation in addition to the pathology laboratory. If a core biopsy is performed as a part of the patient's clinical care, extra cores will be obtained for surgical oncology laboratory, in addition to the cores necessary for clinical care. All cores will be obtained through the same needle to avoid the need of additional punctures and to minimize associated risks.

Tumor tissue will be used for several specific purposes. Pre-treatment biopsies will be used to evaluate potential markers of durable response, in addition to staining for p16ink4a and RB. This will include the analysis of phospho-RB, Cyclin D1, Cyclin E1, Cyclin E2, and p27Kip1 by immunohistochemistry. These proteins have been functionally associated with the response to CDK4/6 inhibitors. We will also assess baseline features of tumor proliferation by Ki67 and phospho-histone H3 staining and cleaved caspase 3 as a marker of tumor cell death. In parallel, if there is sufficient material we will employ RNA sequencing to delineate baseline features of tumor tissue. The molecular features of the tumor from RNA sequencing will be analyzed for association with PFS and other clinical features of disease to explore markers of response. We will use the post-treatment biopsies to determine the effect of LEE011 on tumor markers discussed above and by RNA sequencing. These studies will enable us to evaluate whether LEE011 is acting upon its targets in the tumor and to infer response markers with clinical outcome.

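### The optional second biopsy has conflicting dates and no limit on time since the last LEE011 dose, so a negative target-engagement result could not be told apart from washout

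*Combined protocol and SAP*

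**What the plan says.** Section 6.3 sets the dosing calendar: "LEE011 will be given orally once a day on days 1-21 of a 28 day cycle", with days 22-28 off drug.

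The timing of the second biopsy appears in four places:

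- **Section 7.3.2:** it "will be performed between Weeks 8 and 9 post initial treatment of LEE011". The patient must have had 21 consecutive days of LEE011 and at least one chemoembolization. No condition is set on how recent the last dose must be.
- **Table 7.1, footnote 7:** "it will be performed during the 8th and 9th week of after initiating treatment of LEE011". The same footnote says "LEE011 should be held for 24-48 hours prior to and after the second biopsy", that held doses are not replaced, and that they are noted in the diary.
- **Section 11:** "between eight and nine weeks after the initiation of LEE011 (research only".
- **Table 7.1, tissue-collection row:** the second mark falls under Cycle 2 Day 1, which is day 29, and carries footnote 7.

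The biopsy is optional, Phase II only and for research. Section 11 says the tissue studies will allow the team to "evaluate whether LEE011 is acting upon its targets in the tumor", using phospho-RB, Ki67, other immunohistochemical markers and RNA sequencing.

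**The concern.** A sample meant to show whether a drug acts on its target should be taken at a known point in the dosing cycle, when the drug is present. Here the dates are counted in calendar weeks, and those weeks straddle the planned rest period and the start of re-accumulation. One patient could be biopsied a day after the last dose of a full dosing block and another at the end of a drug-free week, and both would count as on schedule.

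If phospho-RB or Ki67 is not reduced, the reader cannot tell whether LEE011 failed to reach its target or had been cleared. Section 1.5 adds a further difficulty, because it reports raised Ki67 after chemoembolization itself. Patients would be consenting to an invasive, research-only procedure whose negative result has no clear meaning.

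**Working it through.** **Calendar, assuming no interruptions.** Cycle 2 dosing is days 29-49, rest is days 50-56, and Cycle 3 dosing starts on day 57.

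- Week 8 = days 50-56 = Cycle 2 days 22-28, the rest week.
- Week 9 = days 57-63 = Cycle 3 days 1-7.
- Eight to nine elapsed weeks = about days 57-64 = Cycle 3 days 1-8.
- The table mark, Cycle 2 Day 1 = day 29, the first day after the Cycle 1 rest week.

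The table reading depends on column positions in extracted text. The study-drug row, counted the same way, falls on Day 1 of Cycles 1, 2, 3 and 4+, which supports it.

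**Model.** Section 1.7.4.1 says the mean effective half-life "was 32.6 hours in study CLEE011X2101". I use one compartment with once-daily dosing, k = ln 2 / 32.6 per hour, so the fraction kept over 24 h is r = exp(-24k) = 0.600.

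**Check against the protocol's own figures.** Accumulation = 1/(1 - r) = 1/0.400 = 2.5, inside the stated 2- to 3-fold. After 8 daily doses the fraction of steady state is 1 - r^8 = 1 - 0.017 = 0.983, which agrees with steady state by about day 8.

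**Level at biopsy, as a fraction of the 24 h steady-state trough.**

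- Rest week, day 50 + j, last dose on day 49: r^j.
- Cycle 2 Day 1, and Cycle 3 Day 1 before dosing: r^7 = 0.03.
- Cycle 3, day 57 + n, 24 h hold: (1 - r^n) + r^(7+n).
- Cycle 3, day 57 + n, 48 h hold: r(1 - r^(n-1)) + r^(7+n).

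| Day | Cycle day | 24 h hold | 48 h hold |
|---|---|---|---|
| 29 | C2D1 | 3% | 3% |
| 50 | C2D22 | 100% | 60% |
| 51 | C2D23 | 60% | 60% |
| 52 | C2D24 | 36% | 36% |
| 53 | C2D25 | 22% | 22% |
| 54 | C2D26 | 13% | 13% |
| 55 | C2D27 | 8% | 8% |
| 56 | C2D28 | 5% | 5% |
| 57 | C3D1 | 3% | 3% |
| 58 | C3D2 | 42% | 2% |
| 59 | C3D3 | 65% | 25% |
| 60 | C3D4 | 79% | 39% |
| 61 | C3D5 | 87% | 47% |
| 62 | C3D6 | 92% | 52% |
| 63 | C3D7 | 95% | 55% |

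Worked example, day 58 (n = 1): with a 24 h hold, 0.400 + 0.017 = 0.42. With a 48 h hold, 0 + 0.017 = 0.02.

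**Summary over days 50-63.** The mean is 50% (24 h hold) or 31% (48 h). Days below half of trough number 7 of 14 or 10 of 14. Week 9 alone averages 66% or 32%.

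**Sensitivity to an assumed half-life of 20 to 50 h.** The window mean is 50-52% (24 h hold) or 22-38% (48 h). Day 29 is 0-10%. Day 53 is 8-37% and day 57 is 0-10%.

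**Comparator.** A biopsy 24 h or 48 h after the last dose of a full dosing block is at 100% or 60% of trough. With half-lives of 20 to 50 h, the 48 h figure is 44-72%.

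**The case against.** The other side has several good points.

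- **The window is not uniformly off drug.** Days 50-51 keep 60-100% of trough, and with a 24 h hold days 59-63 keep 65-95%. A reader might infer from the rest-week overlap that the biopsy samples tumour largely off drug and so cannot show target engagement. The arithmetic does not support that; exposure is mixed. This point stands.
- **The elapsed-time reading avoids the rest week.** Sections 7.3.2 and 11 can be read as about days 57-64. The hold, with its diary entry for held doses, also presumes a patient who is dosing. This stands for those sections, but footnote 7 plainly brings in days 50-56. Even in Cycle 3, days 2-7 span 42-95% with a 24 h hold or 2-55% with a 48 h hold.
- **Cycle 2 Day 1 may be only a misplaced mark.** It carries footnote 7, so it is not an independent instruction. That is fair, but staff who schedule from the table would biopsy at about 3% of trough.
- **Plasma is not tumour.** The half-life is a plasma figure from another study. The documents give no tumour concentration, no exposure threshold and no duration of marker suppression. This stands: the percentages describe exposure, not inhibition.
- **The last dose is probably recoverable.** Held doses go in the diary, which is reviewed each cycle. That helps, but no analysis is planned that uses the interval.
- **The actual calendar moves.** Cycle starts can follow the visit after chemoembolization, and a general window of 3 days either way may apply. This weakens the nominal dates and makes a fixed interval from the last dose more useful.

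**Conclusion.** The concern holds in limited form. The four statements of timing conflict, and none controls time since the last dose. On the protocol's half-life, exposure at biopsy could lie anywhere from about 2% to 100% of steady-state trough, with 22% or less on days 53-57 and about 3% at the table's mark. A positive target-engagement finding would still be informative. A negative one would be ambiguous, and a pooled estimate would average samples taken on and off drug.

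A reader might go further and infer that secondary objective 2.2.3 cannot be answered. The documents do not support that. The objective also covers baseline tissue and plasma or serum, and Section 11 relates baseline molecular features to PFS; neither depends on this biopsy's date. Only the pharmacodynamic question is affected. The primary PFS analysis is untouched.

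The size rests on uninterrupted 28-day cycles, one-compartment decay, a plasma half-life from another study, and the column reading of Table 7.1. The calendar overlap in footnote 7 needs only the first of these, and the absence of a last-dose rule needs none of them.

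**What to change.** - Reconcile Table 7.1, its footnote 7, Section 7.3.2 and Section 11 to a single timing.
- Define the same optional biopsy relative to the last LEE011 dose of a dosing block instead of by calendar week. One example is the end of the Cycle 2 block, so that the existing 24-48 h interval falls at the start of the rest week (days 50-51 on the nominal calendar), at about 60-100% of trough. State whether the general 3-day window applies: three days after day 51 is day 54, at 13%.
- Record the date and time of the last dose before each biopsy.
- State that post-treatment markers will be analysed with that interval taken into account, and that samples outside the defined interval will be reported separately.

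**Cost.** Wording changes, one added data field and no extra procedure. The real price is a narrower scheduling window for radiology, so some consenting patients may miss it. If the biopsy is placed inside a dosing block instead, some doses are skipped under the existing hold. The length of the hold and the safety conditions for biopsy are clinical matters and are not questioned here.
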